2.6 POOLABILITY ANALYSIS

A poolability analysis will be performed on the primary endpoint to test for a differential treatment effect across study centres. The primary endpoint will be summarized by study centre. Poolability will be assessed using a logistic regression model. The logistic regression model will include a covariate for the treatment arm, study centre, and interaction effect of treatment by centre. The p-value for the interaction effect will be provided. These analyses will be performed for the ITT population. The LOCF method will be used, imputing missing Week 12 urine leakage with the most recent value collected. A single centre will be used to pool small sites (<4 subjects) for the logistic regression.

2.7 SUBGROUP ANALYSIS

Subgroup analyses will be performed on the primary endpoint (“significant improvement” following a provocative pad weight test at 12 weeks) to test for differential treatment effects across baseline subgroups. Subgroups will be derived for the following parameters: race (white versus non-white), BMI [underweight (< 18.5), normal (18.5 to < 25), overweight (25 to < 30), obese (≥ 30)], baseline severity of stress urinary incontinence, and average intensity of the stimulation delivered during the 12-week treatment programme [low (≤ 30 and ≤ 25 for Vital Compact and iTouch Sure, respectively), medium (> 30 to ≤ 60 and > 25 to ≤ 50), high (> 60 to ≤ 90 and > 50 to ≤ 75), and very high (> 90 and > 75)]. Descriptive statistics will be provided for the primary endpoint for each subgroup. These summaries will be presented for the ITT population using observed data (with no imputation for missing data) and using LOCF to impute missing values.

Logistic regression models will be used to statistically evaluate the effect of the subgroups on the primary endpoint. Specifically, the logistic regression model will include a covariate for the treatment arm, subgroup, and interaction effect of treatment by subgroup. The p-value for the interaction effect will be provided. These analyses will be performed for both the ITT and PP populations. The LOCF method will be used, imputing missing Week 12 urine leakage with the most recent value collected.

The change in urine leakage on the provocative pad weight test at Week 12 will also be summarized in the ITT population for these subgroups. No imputation will be used for missing data.

3 DERIVED VARIABLES

3.1 URINE LEAKAGE AND SIGNIFICANT IMPROVEMENT FROM PROVOCATIVE PAD WEIGHT TEST

The urine leakage from the provocative pad weight test is based on the increase in the weight of pad (including packaging) after the provocative pad weight test. ‘Significant improvement’ is defined as greater than 50% reduction in urine leakage from baseline.

3.2 URINE LEAKAGE FROM 24-HOUR PAD WEIGHT TEST

The urine leakage from the 24-hour pad weight test is based on the increase in the weight of 8 pads (including packaging) after 24 hours of collection. If fewer than 8 pads are returned, the urine leakage can only be determined if the missing pads were unused; in this case, the return weight is adjusted by the weight of the missing pads (where the average weight of one single dry pad with packaging is 16.7 g).

The 24-hour pad weight test collects urine leakage across three consecutive 24-hour periods at each timepoint. The average of the 24-hour periods at each timepoint will be used for the analysis of this data.

3.3 7-DAY DIARY ENDPOINTS

The number of incontinence episodes (accidental leaks) and the number of pads used in each 24-hour period were to be collected for 7 days prior to Baseline and Weeks 4, 12, and 26. The analyses will be based on the average values from all entries in the 7 day period.

3.4 SEVERITY OF STRESS URINARY INCONTINENCE

The severity of stress urinary incontinence will be defined as dry (< 1.3g), mild (1.3g to < 20g), moderate (20g to < 75g) and severe ($\geq 75g$), based on the 24-hour pad weight test (O'Sullivan, 2004).

3.5 INCONTINENCE QUALITY OF LIFE QUESTIONNAIRE

The Incontinence Quality of Life Questionnaire (I-QOL) consists of 22 items, all of which are rated on a response scale with five categories (1=extremely to 5=not at all) (Patrick, 1999). I-QOL Total Score will be assessed using the responses from all 22 items. Three subscales will also be assessed:

- I-QOL Avoidance & Limiting Behaviors (Questions 1, 2, 3, 4, 10, 11, 13, and 20)
- I-QOL Psychosocial Impacts (Questions 5, 6, 7, 9, 15, 16, 17, 21, and 22)
- I-QOL Social Embarrassment (Questions 8, 12, 14, 18 and 19)

The I-QOL total and its subscale scores are computed by adding each non-missing item's response, subtracting the lowest possible score and dividing that sum by the possible raw score range. The scores are then transformed to have a range from 0 (poor quality of life) to 100 (maximum quality of life). The formula used to compute the transformed score is:

$$Scale\ Score = \frac{sum\ of\ the\ items\ -\ lowest\ possible\ score}{possible\ raw\ scale\ score\ range} * 100$$

The I-QOL Total Score will be set to missing if more than three items are left unanswered, and the subscales will be set to missing if more than one item is left unanswered.

3.6 PELVIC ORGAN PROLAPSE/URINARY INCONTINENCE SEXUAL QUESTIONNAIRE

The Pelvic Organ Prolapse/Urinary Incontinence Sexual Questionnaire (PISQ-IR) is a questionnaire designed to assess subscales separately for sexually active versus non-active subjects (Rockwood, 2013).

The following subscales are defined for sexually active subjects:

- Arousal and Orgasm (Questions 7, 8a, 10, and 11)
- Partner-Related (Questions 13, 14a, and 14b)
- Condition-Specific (Questions 8b, 8c, and 9)
- Global Quality Rating (Questions 19a, 19b, 19c, and 20a)
- Condition Impact (Questions 18, 20b, 20c, and 20d)

- Desire (Questions 15, 16, and 17)

The following subscales are defined for subjects that are not sexually active:

- Partner-Related (Questions 2a and 2b)
- Condition-Specific (Questions 2c, 2d, and 2e)
- Global Quality Rating (Questions 4a, 4b, 5a, and 6)
- Condition Impact (Questions 3, 5b, and 5c)

Responses to some questions must be reversed prior to scoring. The new values are obtained by subtracting the original response from the maximum value plus 1. For an item with 5 responses, this means a response of 1 becomes a 5, 2 becomes a 4, etc. The following questions must be reversed: 2 (a, b, c, d, e), 5 (a, b, c), 8 (b,c), 9, 11, 14 (a,b), 16, 17, 18, 19 (a,b,c). If Question 11 is missing and the checkbox is checked, a value of 5 will be used for the scoring.

The PISQ-IR subscale scores are computed by adding each non-missing item's response, subtracting the lowest possible score and dividing that sum by the possible raw score range. The scores are then transformed to have a range from 0 (worst) to 100 (best). The formula used to compute the transformed score is:

$$\text{Scale Score} = \frac{\text{sum of the items} - \text{lowest possible score}}{\text{possible raw scale score range}} * 100$$

These subscale scores require a minimum of two non-missing responses, except the Not Sexually Active - Partner-Related subscale which requires only one. If the requirement is not met, the subscale score will be set to missing.

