14.6 Appendix VI. PISQ-IR questionnaire

Appendix A:

PISQ-IR: Sexual Function for Women with: POP, Urinary Incontinence and/or Fecal Incontinence

For More Information or Questions
Email: [contact]

Q1 Which of the following best describes you:

Not sexually active at all 1 → Go to item Q2 (Section 1)

Sexually active with or without a partner 2 → Skip to item Q7 (Section 2)

Section 1: For those who are not Sexually Active

 If you engage in sexual activity please check this box and skip to Page 3

Q2 The following are a list of reasons why you might not be sexually active, for each one please indicate how strongly you agree or disagree with it as a reason that you are not sexually active.

	STRONGLY AGREE	SOMEWHAT AGREE	SOMEWHAT DISAGREE	STRONGLY DISAGREE
a No partner	 ¹	 ²	 ³	 ⁴
b No Interest	 ¹	 ²	 ³	 ⁴
c Due to bladder or bowel problems (urinary or fecal incontinence) or due to prolapse (a feeling of or a bulge in the vaginal area)	 ¹	 ²	 ³	 ⁴
d Because of my other health problems	 ¹	 ²	 ³	 ⁴
e Pain	 ¹	 ²	 ³	 ⁴

Q3 How much does the fear of leaking urine and/or stool and/or a bulging in the vagina (either the bladder, rectum or uterus falling out) cause you to avoid or restrict your sexual activity?

1 Not at All

2 A Little

3 Some

4 A Lot

Q4 For each of the following, please circle the number between 1 and 5 that best represents how you feel about your sex life.

	RATING					
a. Satisfied	1	2	3	4	5	Dissatisfied
b. Adequate	1	2	3	4	5	Inadequate

Q5 How strongly do you agree or disagree with each of the following statements:

	STRONGLY AGREE	SOMEWHAT AGREE	SOMEWHAT DISAGREE	STRONGLY DISAGREE
a. I feel frustrated by my sex life	 ¹	 ²	 ³	 ⁴
b. I feel sexually inferior because of my incontinence and/or prolapse	 ¹	 ²	 ³	 ⁴

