c. I feel angry because of the impact that incontinence and/or prolapse has on my sex life	 ¹	 ²	 ³	 ⁴

Q6 Overall, how bothersome is it to you that you are not sexually active?

1 Not at All
2 A Little
3 Some
4 A Lot

End of Items for Not Sexually Active

PISQ-IR 3

Section 2: For Those Who are Sexually Active

The remaining items in the survey are about a topic that one is not often asked to report on in a survey please answer as honestly and clearly as you possibly can.

Q7 How often do you feel sexually aroused (physically excited or turned on) during sexual activity?

- 1 Never
- 2 Rarely
- 3 Sometimes
- 4 Usually
- 5 Always

Q8 When you are involved in sexual activity, how often do you feel each of the following:

	NEVER	RARELY	SOMETIMES	USUALLY	ALMOST ALWAYS
a. Fulfilled	 ¹	 ²	 ³	 ⁴	 ⁵
b. Shame	 ¹	 ²	 ³	 ⁴	 ⁵
c. Fear	 ¹	 ²	 ³	 ⁴	 ⁵

Q9 How often do you leak urine and/or stool with any type of sexual activity?

- 1 Never
- 2 Rarely
- 3 Sometimes
- 4 Usually
- 5 Always

Q10 Compared to orgasms you have had in the past, how intense are your orgasms now?

- 1 Much less intense
- 2 Less intense
- 3 Same intensity
- 4 More intense
- 5 Much more intense

Q11 How often do you feel pain during sexual intercourse? (If you don't have intercourse check this box and skip to the next item.)

- 1 Never
- 2 Rarely
- 3 Sometimes
- 4 Usually
- 5 Always

Q12 Do you have a sexual partner?

- 1 Yes → Go to Q13
- 2 No → Skip to Q15

Q13 How often does your partner have a problem (lack of arousal, desire, erection ,etc.) that limits your sexual activity?

- 1 All of the time
- 2 Most of the time
- 3 Some of the time
- 4 Hardly ever/Rarely

Q14 In general, would you say that your partner has a positive or negative impact on each of the following:

	VERY POSITIVE	SOMEWHAT POSITIVE	SOMEWHAT NEGATIVE	VERY NEGATIVE
a. Your sexual desire	 ¹	 ²	 ³	 ⁴

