b. The frequency of your sexual activity	 ¹	 ²	 ³	 ⁴

Q15 When you are involved in sexual activity, how often do you feel that you want more?

- 1 Never
- 2 Rarely
- 3 Sometimes
- 4 Usually
- 5 Always

Q16 How frequently do you have sexual desire, this may include wanting to have sex, having sexual thoughts or fantasies, etc.?

- 1 Daily
- 2 Weekly
- 3 Monthly
- 4 Less often than once a Month
- 5 Never

Q17 How would you rate your level (degree) of sexual desire or interest?

- 1 Very high
- 2 High
- 3 Moderate
- 4 Low
- 5 Very low or none at all

Q18 How much does the fear of leaking urine, stool and/or a bulging in the vagina(prolapse) cause you to avoid sexual activity?

- 1 Not at All
- 2 A Little
- 3 Some
- 4 A Lot

Q19 For each of the following, please circle the number between 1 and 5 that best represents how you feel about your sex life.

RATING						
a	Satisfied	1	2	3	4	5
b	Adequate	1	2	3	4	5
c	Confident	1	2	3	4	5

Dissatisfied Inadequate Not Confident

Q20 How strongly do you agree or disagree with each of the following statements:

	STRONGLY AGREE	SOMEWHAT AGREE	SOMEWHAT DISAGREE	STRONGLY DISAGREE
a. I feel frustrated by my sex life	 ¹	 ²	 ³	 ⁴
b. I feel sexually inferior because of my incontinence and/or prolapse	 ¹	 ²	 ³	 ⁴
c. I feel embarrassed about my sex life	 ¹	 ²	 ³	 ⁴
d. I feel angry because of the impact that incontinence and/or prolapse has on my sex life	 ¹	 ²	 ³	 ⁴

14.7 Appendix VII. Medical, Epidemiologic and Social Aspects of Aging Urinary Incontinence (MESA) Questionnaire

If you have any urine leakage, the questions below will be asking you about urination and activities that cause some people to lose urine. Please place a tick in the box that best describes you and your situation.

STRESS INCONTINENCE QUESTIONS

1) Does coughing gently cause you to lose urine?	 Often (3)  Sometimes (2)  Rarely (1)  Never (0)

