2.2 SUBJECT ACCOUNTING AND BASELINE CHARACTERISTICS

The ITT and PP populations will be summarized for the following demographic and baseline characteristics:

- age
- race and ethnicity

- menopause status
- height, weight, and BMI
- general medical history (ITT population only)
- physical examination findings (ITT population only)
- prior and concomitant medications (ITT population only)

Baseline assessments of stress urinary incontinence data will be summarized for the ITT and PP populations. Incontinence Quality of Life Questionnaire (I-QOL) scores and Pelvic Organ Prolapse/Urinary Incontinence Sexual Questionnaire (PISQ-IR) scores will be summarized for the ITT and PP populations. Study completion status and primary reason for discontinuation will be summarized for the ITT population. Medical history will be coded using Medical Dictionary for Regulatory Activities (MedDRA) and medications will be coded using the World Health Organization Drug dictionary (WHO Drug).

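### SAP 3.6 labels every PISQ-IR subscale 0 (worst) to 100 (best), but its reversal list gives 0 for the best answers on at least three of the four not-sexually-active subscales

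*SAP*

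**What the plan says.** SAP 3.6 defines six PISQ-IR subscales for sexually active women and four for women who are not. Four names serve both sections: Partner-Related, Condition-Specific, Global Quality Rating and Condition Impact. A single scoring rule covers all ten, and its direction is stated once: "The scores are then transformed to have a range from 0 (worst) to 100 (best".

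The reversal list begins "The following questions must be reversed: 2 (a, b, c, d, e), 5 (a, b, c" and continues with items from the sexually active section only (8b-c, 9, 11, 14a-b, 16, 17, 18, 19a-c). Items 3, 4a, 4b and 6 of the not-active section are therefore scored as printed.

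PISQ-IR is reported in two places. SAP 2.2 says that "Pelvic Organ Prolapse/Urinary Incontinence Sexual Questionnaire (PISQ-IR) scores will be summarized for the ITT and PP populations" as a baseline characteristic. SAP 2.3.4 lists mean change from baseline to Week 12 among the additional endpoints. SAP section 4, on changes from the protocol, does not mention PISQ-IR scoring.

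**The concern.** A reversal list should make every item in a scale point the way the label says. In the not-active section the items left alone already have high values for bad answers. The items that are reversed start with high values for good answers and end with high values for bad ones. Every item in the three clear scales then points to high = worse, under a label that says high = better.

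The clearest sign is that the two sections share questions that the list treats in opposite ways. "Q4 For each of the following, please circle the number between 1 and 5 that best represents how you feel about your sex life" (not active) is not reversed. "Q19 For each of the following, please circle the number between 1 and 5 that best represents how you feel about your sex life" (active) has the same stem, and its satisfied and adequate items have the same anchors and codes, yet it is reversed.

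At stake is the sign of a reported patient outcome. A programmer who follows SAP 3.6 exactly, and a reader who trusts its label, would take improvement in a non-active woman for worsening, and the reverse. Rows with the same name in the two sections would run in opposite directions without warning.

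**Working it through.** **Inputs.** Item wording and codes come from Protocol Appendix VI. Subscale membership, reversal list and formula come from SAP 3.6.

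- Reversed value = (item maximum + 1) - response.
- Score = 100 × (sum of items - lowest possible sum) / (highest possible sum - lowest possible sum).

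**Step 1: direction of each not-active item after the list is applied.**

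| Item | Printed coding | Reversed? | High value then means |
|---|---|---|---|
| 2c-e | 1 strongly agree to 4 strongly disagree with a reason for inactivity | yes | agreement (worse) |
| 3 | 1 not at all to 4 a lot | no | worse |
| 4a, 4b | 1 satisfied/adequate to 5 dissatisfied/inadequate | no | worse |
| 5a-c | 1 strongly agree to 4 strongly disagree with a negative statement | yes | agreement (worse) |
| 6 | 1 not at all to 4 a lot | no | worse |

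Item 3 is "Q3 How much does the fear of leaking urine and/or stool and/or a bulging in the vagina" (as a cause of avoiding or restricting activity). Item 6 is "Q6 Overall, how bothersome is it to you that you are not sexually active".

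**Step 2: scores for the best and worst answers, not-active section.**

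| Scale | Best answers | Worst answers |
|---|---|---|
| Condition-Specific (2c-e) | (3-3)/9 = 0 | (12-3)/9 = 100 |
| Global Quality Rating (4a, 4b, 5a, 6) | (4-4)/14 = 0 | (18-4)/14 = 100 |
| Condition Impact (3, 5b, 5c) | (3-3)/9 = 0 | (12-3)/9 = 100 |
| Partner-Related (2a, 2b), if agreement is unfavourable | (2-2)/6 = 0 | (8-2)/6 = 100 |

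The same calculation on the six sexually active scales gives 100 for the best answers and 0 for the worst in all six. The stated 0 to 100 range is reproduced everywhere; the stated direction is reproduced only in the active section.

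**Step 3: improvement of one answer category on every item.**

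| Scale | Not active | Active |
|---|---|---|
| Condition-Specific | -3/9 = -33.3 | +3/12 = +25.0 |
| Global Quality Rating | -4/14 = -28.6 | +4/15 = +26.7 |
| Condition Impact | -3/9 = -33.3 | +4/12 = +33.3 |

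**Step 4: identical questions in both sections.** Five pairs share wording and codes: 4a/19a, 4b/19b, 5a/20a, 5b/20b and 5c/20d. In all five the list reverses exactly one member. Items 3 and 18 form a nearly identical sixth pair, in which only 18 is reversed.

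As an illustration, take only the three Global Quality items common to both sections. This three-item score is not a SAP scale; its range is 4 + 4 + 3 = 11. Suppose satisfied and adequate each go from 4 to 2, and frustrated goes from somewhat agree (2) to somewhat disagree (3).

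- Not active: (4+4+3-3)/11 = 72.7 to (2+2+2-3)/11 = 27.3, a change of -45.5.
- Active: (2+2+2-3)/11 = 27.3 to (4+4+3-3)/11 = 72.7, a change of +45.5.

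**Step 5: would another list restore the label?** With no reversal at all, the best answers score (7-4)/14 = 21.4 on not-active Global Quality and (9-3)/9 = 66.7 on Condition Impact, so some reversal is needed. Reversing 3, 4a, 4b and 6, and leaving 2a-e and 5a-c as printed, gives 100 for best and 0 for worst on all four not-active scales (Partner-Related on the same reading as above).

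**The case against.** The strongest reply is that this is a label, not a scoring fault. The list aligns the not-active items with one another, so the scores are usable and the size of any change or group difference is correct. The cited scoring paper may intend high = worse in this section, in which case a single parenthesis is too broad. That may be so, and the documents cannot settle it. It does not rescue SAP 3.6, which applies one direction to both sections.

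A second reply is that little depends on it. Protocol 10.3.8 and SAP 2.3.4 make PISQ-IR descriptive with no formal test, Protocol 10.3.8 rules out labelling claims, and it is not among the 11 key secondary endpoints. SAP 3.6 scores the two sections separately, and nothing in the plan pools them. All of this stands and limits the consequence. The misreading needs no pooling, however: a table of the not-active scales read by the stated label is enough.

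A third reply is that direction is partly a judgement. For "Partner-Related (Questions 2a and 2b" it is, because lacking a partner or interest need not be bad. Item 2d (other health problems as the reason) is also less clear than 2c and 2e, and item 15 in the active Desire scale needs a reading too. None of this touches Global Quality Rating or Condition Impact, and 2c and 2e fix the direction of Condition-Specific.

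**Conclusion.** The concern holds. As written, the SAP 3.6 label and reversal list contradict each other for Condition-Specific, Global Quality Rating and Condition Impact in women who are not sexually active, and for Partner-Related as well if agreement there is read as unfavourable. The reversal of direction is complete: 0 where the label promises 100, and 100 where it promises 0.

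The result rests only on the printed item codes and the SAP's own rules. Its practical weight depends on how many women are not sexually active, which the documents do not give. It affects the reading of the baseline PISQ-IR summaries and the Week 12 change, and leaves the primary endpoint and the key secondary hierarchy untouched. It should be corrected because it would turn the sign of a listed outcome, but it does not threaten the trial's main conclusion.

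**What to change.** Before unblinding, check the scoring paper that SAP 3.6 cites and make the label and the list agree for the not-active scales.

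- **Simplest change:** state the direction by section, with the active scales running from 0 (worst) to 100 (best) and the not-active scales from 0 (best) to 100 (worst). No score changes.
- **Only if the cited source supports it:** report 100 minus the score for the not-active scales. With complete answers this equals the alternative list in step 5 of the working. With missing items the two agree only if the lowest sum and the range are taken over the answered items, so the SAP would have to say so.
- **In either case:** say how the not-active Partner-Related scale is to be read, and print the direction on each PISQ-IR table.

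The cost is one sentence in SAP 3.6 and a table footnote, plus one line of derivation code if scores are reflected. No new data are needed.

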3.7 DEVICE USE

Subjects randomized to the Vital Compact device are to use the device once per day for five days each week for the 12-week period. Subjects randomized to the itouch Sure Pelvic Floor Exerciser are to use the device once per day for the 12-week period. Subjects are to complete a daily record of device use, including their first in office session.

3.7.1 AVERAGE NUMBER OF SESSIONS PER WEEK

The average number of sessions per week is calculated as

$$\text{Average Number of Sessions per Week} = \frac{\text{number of sessions used}}{\text{duration of treatment}} * 7$$

where the number of sessions used is obtained from the daily record and the duration of treatment is the relative day of the Week 12 visit minus 1.

3.7.2 DEVICE USE – PERCENT OF ACTUAL USE

The percentage of actual use (through the usage period) is calculated as

$$\text{Actual Use (\%)} = \frac{\text{number of sessions used}}{\text{number of sessions expected}} * 100$$

where the number of sessions used is obtained from the daily record and the number of sessions expected is based on the relative day of the Week 12 visit. [For itouch Sure subjects, the number of sessions expected is the relative day of the visit minus 1; for Vital Compact subjects, it is the truncated value of $5/7 * (\text{relative day} - 1)$].

3.7.3 DEVICE USE – PERCENT OF TARGET USE

The percentage of target use (through Week 12) is calculated as

$$\text{Target Use (\%)} = \frac{\text{number of sessions used}}{\text{number of sessions prescribed}} * 100$$

where the number of sessions used is obtained from the daily record and the number of sessions prescribed is based on 12 weeks of usage. [For itouch Sure subjects, the number of sessions prescribed is $12 * 7 = 84$; for Vital Compact subjects, it is $5 * 12 = 60$].

